5.9. Rescue Treatment

Patients who show no clinical response to treatment at the EOT visit, as well as patients with evidence of relapse, i.e. *T.b. gambiense* found in any bodily fluid, or of probable relapse at any time during follow-up will receive NECT, an alternative treatment for HAT, as per usual practice in the investigational centre.

The definition of probable relapse disclosed at the 6-month, 12-month or 18month follow-up visit is provided in Table 1.

Rescue treatment for HAT will not be recorded in the "Concomitant Treatment" section of the eCRF, but will be recorded as a comment on the "End of Study" page with the date of treatment start.

Table 1 – Clinical Management of Patients

Visit	Ideal timing of visit after end of treatment	Success	Probabale success	Probable failure	Proven failure
24 hours after EOT	Within 2 days	• Patient alive with no evidence of trypanosomes in any bodily fluid (54)			 Evidence of trypanosomes in any bodily fluid
3 months	3 months ± 1 week	 Patient alive with no evidence of trypanosomes in any bodily fluid (no lumbar puncture at 3 months unless Investigator suspects a relapse) 	 Any reason leading the Investigator to request an additional follow-up visit 	 Signs or symptoms suggestive of HAT and of treatment failure leading to use of rescue treatment 	 Evidence of trypanosomes in any bodily fluid
6 months	6 months ± 2 weeks	 Patient alive with no evidence of trypanosomes in any bodily fluid and CSF WBC ≤ 20/µL 	 CSF WBC between 20 and 50/µL and additional follow-up visit requested within 1 to 3 months Any reason leading the Investigator to request an additional follow-up visit 	 CSF WBC ≥ 50/µL (36) Neurological signs or symptoms leading to use of rescue treatment 	 Evidence of trypanosomes in any bodily fluid
12 months	12 months ± 4 weeks	 Patient alive with no evidence of trypanosomes in any bodily fluid and CSF WBC ≤ 20/µL 	 CSF WBC > 20/µL and clinically non-significant increase as compared to previous value(s) CSF WBC > 20/µL and < 50/µL and reduced as compared to previous value(s) Any reason leading the Investigator to request an additional follow-up visit within 1 to 3 months 	 CSF WBC ≥ 50/µL Signs or symptoms suggestive of HAT and of treatment failure leading to use of rescue treatment 	 Evidence of trypanosomes in any bodily fluid

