9.2. Handling of Missing Data and Patients Lost to Follow-up

The primary endpoint is the outcome, i.e. success or failure, of treatment at the 12-month visit. If the outcome at the 12-month visit is missing, the **primary method of imputation** will consist in imputing a probable success (considered as a success) to patients who attended the visit but who refused the lumbar puncture planned for the visit, who showed no signs or symptoms of HAT at 12 months, who did not subsequently report any symptoms of relapse and for whom the outcome was considered as favourable at the last available assessment (42). If these criteria are not fulfilled, the patients will be considered as treatment failures. The outcome for patients lost to follow-up from the 12-month visit onwards will also be considered as a failure.

Two additional methods for imputing missing data will be used.

The **second method** will consist in imputing failure if there is no lumbar puncture at 12 months or later.

In the **third method**, missing data will not be imputed. All patients for whom an assessment is available at a given timepoint will be included in the estimate of the success rate at that timepoint. If a value is missing at an intermediate visit,

followed by a success or a failure at one of the subsequent visits, the status at the subsequent visit will prevail over the status at the intermediate visit. In the Kaplan-Meier approach, the observation is censured at the first missing outcome, provided that all subsequent outcomes are also missing.

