9.8. Efficacy Analysis

9.8.1. Primary Efficacy Analysis

Primary Efficacy Endpoint

The primary efficacy endpoint is the. success or failure, at 12 months after the final treatment intake. The patient's treatment will be a success if there is no evidence of trypanosomes in any bodily fluid, and the WBC count in the CSF is $\leq 20/\mu$ L. Patients with no parasitological evidence of relapse, but with a CSF WBC count > 20/µL or who, in the opinion of the Investigator, require rescue treatment, will be considered to be probable relapses and therefore as failures. Death due to any cause or use of rescue medication will be considered as a relapse, i.e. a failure. A patient who attends the follow-up visit at 12 months or later and who

refuses to undergo lumbar puncture, but who has no signs or symptoms of HAT and for whom the outcome was assessed as favourable at the last assessment will be considered as a probable cure, i.e. a success, unless signs of relapse are detected on any assessment up to 18 months.

Primary Analysis

The primary analysis will be performed on the ITT population.

The primary endpoint is the success or failure of treatment, as defined above.

The primary analysis of success or failure will be performed at 12 months of follow-up.

The primary test is an exact test derived from the exact confidence interval (CI) of the success rate at 12 months.

Two sets of statistical hypotheses will be tested simultaneously:

 H_{0A} : the true success rate is equal to or less than 80%, which is considered to be unacceptable.

H_{1A}: the true success rate is greater than 80%.

 H_{0B} : the true success rate is equal to or greater than 92%, which is the target or expected success rate for fexinidazole.

H_{1B}: the true success rate is less than 92%.

If H_{0A} is rejected, then the success rate is significantly greater than 80% and the estimated rate is consistent with a rate of 92%. In this case, H_{0B} is automatically accepted, but not necessarily true.

If H_{0B} is rejected, then the success rate is significantly less than the target of 92%, and the estimated rate is consistent with the unacceptable rate of 80%. In this case, H_{0A} is automatically accepted, but not necessarily true.

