9.8.3. Secondary Efficacy Analyses

- The secondary analysis will be performed on the success rate at month 18.
- determine whether the success rate of treatment with fexinidazole varies depending on the stage of the disease, i.e. stage 1 versus early stage 2 versus late stage 2, using a Fisher exact test to compare the rates observed with the 3 different stages.

If the difference between the 3 stages is significant, then the exact 95% CI of each success rate at 12 months will be calculated, and the stage that is responsible for the heterogeneity will be identified. The stage responsible for the heterogeneity will be separated from the other 2 stages, and the lower limit of the 95% CI of each of the 2 subgroups will be compared to the limit of 75%, which is slight higher than the success rate of melarsoprol at 12 months. A limit lower than 80%, i.e. 75% instead of 80%, was chosen because the sample size in each subgroup will be smaller, which will have an impact on the statistical power of each comparison. The upper limit of the CI of the success rate in patients with stage-1 HAT should be consistent with (greater than or equal to) the rate of 93%, which is the

historical success rate of pentamidine (61). The upper limit of the CI of the success rate in patients with stage-2 HAT should be consistent with the rate of 94%, which is the historical success rate of NECT.

- The correlation between the success rate and the WBC count in the CSF will be estimated using a logistic regression. The WBC count will be a quantitative covariate. Another analysis will be performed using a logistic regression with a random intercept to take into account the centre effect. A trend test will also be performed using the Bartholomew's test. Another analysis will be performed after pooling patients with late stage-2 HAT treated with fexinidazole in the pivotal study with patients in this study. The correlation between the success rate and the baseline WBC count will be adjusted with a logistic regression model using the centre as covariate.
- The time-course of the cumulative rate of definitive failure (from the start
 of treatment to the definitive failure) will be estimated using the KaplanMeier method, and patients lost to follow-up will be considered as
 censures. The success rate at each timepoint will be estimated and
 compared using a Cochran Q-test. The logistic model for repeated
 measures (Glimmix procedure in SAS[®]) will be used to test the time effect

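### Censoring the Kaplan-Meier curve at the first missed outcome, not the last completed assessment, slightly understates cumulative failure

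*Protocol*

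**What the plan says.** Section 9.2 gives a primary imputation method and two additional ones. Under the third, "missing data will not be imputed", and the rule for the survival curve follows: "In the Kaplan-Meier approach, the observation is censured at the first missing outcome, provided that all subsequent outcomes are also missing". An intermediate gap followed by a later result takes the later status, so the rule applies only to children who never return.

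Section 9.8.3 describes the curve as "The time-course of the cumulative rate of definitive failure", with time running from the start of treatment, and adds that "patients lost to follow-up will be considered as" censored. It does not define definitive failure, and no other section does. Table 1 in section 5.9 uses only probable and proven failure.

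Section 9.8.1 defines failure for the primary endpoint. Children without parasites but with a raised CSF white cell count, or judged to need rescue, "will be considered to be probable relapses and therefore as failures". It also states: "Death due to any cause or use of rescue medication will be considered as a relapse, i.e. a failure".

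**The concern.** Relapse in this trial is detected by examining blood, lymph and CSF at visits: end of treatment, months 3, 6, 12 and 18, and unscheduled returns. Nothing is learned about a child between the last attended visit and the first missed one. Censoring at the missed visit credits the child with failure-free time that was never observed. By the usual convention, a subject censored at an event time still counts as at risk at that time. A child lost after month 6 can therefore sit in the month-12 denominator with no chance of entering the numerator.

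The curve serves the secondary objective of studying how the success rate changes over time. At stake is a failure rate that looks slightly too low on that curve.

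**Working it through.** **The plan's own figures.** The protocol gives no figure for the Kaplan-Meier analysis. Its design figures are 125 children, 80% against 92%, one-sided 0.025, at least 109 successes and power 97.5% (sections 9.1 and 9.8.1). An exact binomial calculation gives a type I error of 0.0243 and power of 0.978, which agrees. None of this depends on the censoring rule.

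**Inputs for the illustration**
- 125 children and a 92% target success rate (sections 9.1 and 9.8.1), so about 0.08 × 125 = 10 failures.
- Assumed, because the protocol gives no such counts: 3 failures found at month 6, 7 at month 12, no other censoring, and L = 6, 12 or 25 children lost after month 6 without failure. The 7 month-12 failures are held fixed as L varies.
- Yardstick: the standard error of the success rate at target, √(0.92 × 0.08 / 125) = 0.0243.

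**Rule as written, lost children kept at risk at month 12.** After month 6, 125 − 3 = 122 children are at risk.

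Cumulative failure = 1 − (122/125) × (1 − 7/122) = 1 − 115/125 = 0.080, whatever the value of L.

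**Censoring at the last completed assessment, month 6.** The lost children leave before month 12.

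Cumulative failure = 1 − (122/125) × (1 − 7/(122 − L)).

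| Lost after month 6 | At risk at month 12 | Cumulative failure | Difference from 8.0% | In standard errors |
|---|---|---|---|---|
| 6 | 116 | 8.3% | 0.3 points | 0.12 |
| 12 | 110 | 8.6% | 0.6 points | 0.25 |
| 25 | 97 | 9.4% | 1.4 points | 0.59 |

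To reach half a standard error, about 22 children (22/125 = 17.6%) would have to be lost in this one interval: 1 − 0.976 × (1 − 7/100) = 0.0923, a shift of 0.0123/0.0243 = 0.51 standard errors.

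**Direction.** Censoring later can only enlarge the risk set at a given failure time. Each hazard step is then equal or smaller, and so is cumulative failure.

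**The case against.** The best defence is that the size depends on date conventions the protocol does not fix. Table 2 in section 6.1 lets the month-12 visit fall between 10 and 16 months after the end of treatment, and no date is assigned to a visit that did not take place. If a missed visit is dated before other children's month-12 failures, the lost child has already left the risk set and the effect shrinks, possibly to nothing. The losses are assumed too, and the protocol provides for tracing and for visits at a new address (sections 6.4 and 8.4). All of this stands as to size. It does not change the direction, and section 9.2 states the rule explicitly rather than leaving it to the analysis plan.

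The curve is also only one of the time analyses. Section 9.8.3 adds a comparison of success rates across timepoints with Cochran's Q and a repeated-measures logistic model. Further, a Kaplan-Meier failure rate below the primary one is partly by design, since children lost and not retrieved are failures in the primary analysis and censored here. That choice is deliberate and is not criticised.

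A reader might infer something stronger: that deaths and rescued probable relapses are censored. The route would be to read definitive failure as Table 1's proven failure (trypanosomes found), to note that Table 1 puts death in neither failure column, and to note that rescue is not entered as concomitant treatment "but will be recorded as a comment on the" End of Study page, so that later outcomes may be absent. On that reading, if 2, 3 or 5 of 10 failures were censored, cumulative failure at month 18 would fall from 8.0% to 6.4%, 5.6% or 4.1%. The documents do not support it. The censoring rule acts only on missing outcomes; sections 2.2.1 and 9.8.1 make death a failure, and 9.8.1 does the same for rescue and probable relapse. Section 9.8.3 names only children lost to follow-up as censored. The rescue comment carries the treatment start date, so the event can be dated. Equating definitive with proven is the reader's own step, and the analysis plan may supply the definition.

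**Conclusion.** The point holds for the censoring date. As written, section 9.2 can keep a lost child in the risk set beyond the last time anyone could have found a failure, and this biases cumulative failure downwards or leaves it unchanged. In the illustration the shortfall at month 12 is 0.3, 0.6 or 1.4 percentage points for 6, 12 or 25 losses after month 6. The figures rest on the assumed failure counts, on the assumed losses, and on lost children being counted at risk at month 12. Different visit dating would give less. At 6 or 12 losses the effect is no more than a quarter of a standard error.

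The undefined event is a request for clarification. It is not evidence that deaths or rescues drop out of the curve: if they count as failures, as 9.8.1 says, the understatement from that source is zero. The consequence is confined to one secondary curve.

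**What to change.** In section 9.2, replace the Kaplan-Meier sentence with one stating that children lost to follow-up or withdrawn without failure are censored at the date of their last completed outcome assessment.

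In section 9.8.3, in the same edit, replace definitive failure with failure as defined in 9.8.1, including death from any cause and use of rescue treatment, each dated when it occurred, and other failures dated at the visit that established them.

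Both are wording changes and need no new data, since assessment dates are collected and the start date of rescue is already recorded. The only downside is that the curve may report a slightly higher cumulative failure rate.

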9.3. Handling of Centres

The primary analysis will not be stratified by centre. However, any variation in the success rate at 12 months between centres will be tested with an exact test. If the hypothesis of homogeneity is not rejected, the overall value of the result of the primary analysis is acceptable. Conversely, if the hypothesis of homogeneity is rejected (H_0), the heterogeneity may be due to atypical centres. The centres responsible for the heterogeneity will be identified and removed form the analysis in order to determine whether the success rate is higher or lower without these centres. The centre effect will also be analysed using the Glimmix procedure in order to study the time course of treatment response.

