• Per-protocol population: all patients with no major protocol violations that could interfere with the efficacy analysis. Sensitivity analyses will be performed on treatment completers, the population of evaluable patients and the per-protocol population. **Analysis** The primary analysis will be performed on the ITT population, by estimating the rate of success or failure at 12 months of follow-up. If the lower bound of the 95% confidence interval is less than or equal to 80% the study will be a failure, otherwise it will be a success. The primary test is an exact test derived from the exact confidence interval of the success rate at 12 months. Sample Size Determination of the sample size was based on the primary analysis. The sample size must be 125 patients having received at least one dose of fexinidazole. The sample size may be 126 patients if two patients are recruited simultaneously at the time of study discontinuation, however, it must not exceed 126 patients.

1. Background and Study Rationale

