9.1. Sample Size Determination

Determination of the sample size was based on the primary analysis (see Section 9.8.1 Primary Efficacy Analysis, p 61). With a sample size of 125 patients, the probability of rejecting H_{0A} ($\pi \le 0.8$) is 97.5% if the true success rate is 92% with a one-sided type-I error of 0.025. The probability of rejecting H_{0B} ($\pi \ge 0.92$) is also 97.5% if the true success rate is 80% with a one-sided type-I error of 0.025. The statistical power achieved is slightly higher than the desired power, and the alpha value obtained is slightly lower than the desired value, due to the discrete distribution of the population. The sample size may be 126 patients who received at least one dose of fexinidazole if two patients are recruited simultaneously at the time of study discontinuation. If the sample size exceeds 126 patients, there is a risk of simultaneously rejecting both H_{0A} and H_{0B}. The sample size should not be less than 125 in order to avoid the risk of not rejecting either hypothesis.

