If the observed success rate is equal to or greater than 87.2% (\geq 109 successes out of 125 patients), or equal to or greater than 110 successes out of 126 patients (if the sample size is equal to 126), then the study is a success since the rate is significantly greater than 80% and consistent with the target success rate of 92%.

Conversely, if the observed success rate is less than 87.2% (\leq 108 successes out of 125patients) or less than 110 successes out of 126 patients, then the study is a failure since the success rate is significantly less than the target rate of 92% and consistent with the unacceptable rate of 80%.

The unacceptable success rate of 80% is greater than the success rate of melarsoprol at 12 months, i.e. 74.8%, because the success rates of the alternative treatments, i.e. NECT and pentamidine, are considerably higher than the rate with melarsoprol, which increases the level of unacceptability.

The target or expected rate of 92% is greater than the expected value of 89% set in the pivotal study, because the success rate is evaluated at 12 months instead of 18 months (expected gain of 1.2%) and also because the success rate reported in the pivotal study is encouraging, since only one failure (a patient whose health status had been poor at inclusion) among 150 patients was observed at the EOT, and no relapses were observed among 30 patients during the 6-month follow-up period (blinded data with an allocation ratio of 2 fexinidazole for 1 NECT).

It should be noted that, in the pivotal study, a 94% success rate was expected for NECT at 18 months, and the margin of acceptable difference was set at 13%. This means that the level of the unacceptable rate for fexinidazole is81% if the success rate for NECT is truly 94%, and 80% if the success rate for NECT was 93%. This also means that the various expectations and limits are consistent across studies.

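### The centre check lets a low-power test decide whether the primary result is acceptable, and otherwise drops centres picked on their outcomes, which tends to raise the success rate near the 92% target

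*Protocol*

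**What the plan says.** Section 9.3 opens with "The primary analysis will not be stratified by centre". It then sets an exact test of whether 12-month success varies between centres, and gives two consequences:

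- If homogeneity is not rejected, "the overall value of the result of the primary analysis is acceptable".
- If it is rejected, the heterogeneity is put down to atypical centres: "The centres responsible for the heterogeneity will be identified and removed". The stated purpose is to learn whether the rate goes up or down without them.

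The section also plans a Glimmix analysis of the centre effect. It gives no level for the test, does not name the exact test, and gives no criterion for which centres count as responsible or how to read the reduced-set rate.

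The primary verdict is fixed elsewhere. Section 9.8.1 states "The primary analysis will be performed on the ITT population" and sets the pass mark at "109 successes out of 125 patients" or more (110 if 126 are treated). The Protocol Summary gives the same rule through the lower 95% confidence limit. Neither place mentions centres.

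**The concern.** Two rules stated in section 9.3 are poor statistics.

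First, failing to reject homogeneity is treated as grounds for accepting the result. That is only as good as the test's power, and with few failures spread thinly over centres the power is low. A centre with clearly worse outcomes would usually go unnoticed, while the text would describe the result as acceptable.

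Second, after a rejection the centres to drop are picked by looking at their outcomes. When success is near 92%, a small centre with no failures is unremarkable, so mostly low centres can stand out. A comparison presented as open in either direction is therefore tilted towards a higher rate. A reader who is shown the reduced-set rate without that warning will take it as better evidence than it is.

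**Working it through.** **Inputs from the protocol.** Sample size: "The sample size must be 125 patients having received at least one dose of fexinidazole" (Protocol Summary; 126 at most). Null hypothesis: "the true success rate is equal to or less than 80"% (9.8.1). Target 92% (9.1, 9.8.1). About 8 centres (4.1), with no cap on patients per site (Table 5).

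**Assumptions not in the protocol.** Test level 0.05; centre-size layouts; Fisher-Freeman-Halton as the exact test; removal of the centre with the largest standardised deviation, either once or repeated until homogeneity is no longer rejected.

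**1. The plan's own figure.** Section 9.1 says the power to reject the 80% null "is 97.5% if the true success rate is 92% with a one-sided type-I error of 0.025". Exact binomial: P(X ≥ 109 | 125, 0.80) = 0.0243 and P(X ≥ 109 | 125, 0.92) = 0.9781. The figure reproduces. The pass mark is sharp: 109/125 has a lower limit of 80.05%, while 108/125 has 79.1% and fails.

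**2. Information available to the test.** Expected failures at target: 125 × 0.08 = 10. Average centre size: 125 / 8 ≈ 16. So each centre has a little over one expected failure.

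**3. Power of the homogeneity test** (simulation; one low centre, the others at 92%):

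| True rate in the low centre | 8 near-equal centres (15-16 each) | Low centre has 10 patients, uneven sizes |
|---|---|---|
| 80% | about 15% | 12% |
| 70% | 37-38% | 27% |
| 60% | 64-66% | 49% |
| 50% | 85% | 68% |

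An example: one centre at 9/16 (56%), the rest at 99/109 (91%), total 108/125. Fisher-Freeman-Halton gives p = 0.09, which section 9.3 would treat as acceptable. The exact Pearson version gives p = 0.03, which would trigger removal. So the choice of exact test alone can change which branch is taken.

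**4. Direction after removal.** The chance that a centre of 16 has no failures at 92% is 0.92^16 = 26%, so a perfect small centre is not an outlier. For a centre of 60 it is 0.92^60 = 0.7%, so a perfect large centre is. Share of rejections in which removal raised the rate:

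- Identical centres at 92%: about 94-100% with equal to moderately uneven sizes. With a largest centre of 40 or 60, uneven layouts gave 85-97% at a mean rate of 92%.
- True rate 80%: about 75-90%, depending on sizes.
- Reverse case: one centre of 40-60 patients at 98-100% and the rest at 80-84%. The rate fell in 74-81% of rejections.

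With identical centres the rise averaged about 2 to 3 percentage points.

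**5. Can the reduced set contradict the verdict?** In a single case, yes. Take 108/125 (86.4%, lower limit 79.1%) with one centre at 8/16 (homogeneity p = 0.015). Removing it leaves 100/109 = 91.7%, lower limit 84.9%.

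**6. How often, with identical centres?** At a true 85%, about 5% of trials trigger the removal. In about 20-35% of those, the reduced-set lower limit exceeds 80% although the trial failed. Product: 0.05 × 0.20 = 1.0% to 0.05 × 0.35 = 1.75%. Direct counts gave 0.9-1.5% of all trials. At a true 80% the figure is 0.3-0.5%, and at 92% about 0.1%.

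**The case against.** The strongest reply is that nothing in the verdict depends on this check. The Protocol Summary and section 9.8.1 fix success or failure on all treated patients, without condition. Section 9.3 describes removal as a look at how the rate moves and does not re-test the reduced set against 80%. This stands. A reader might infer that the plan lets a failed trial be declared a success once an unfavourable centre is dropped. The documents do not support that: the reduced-set rate never replaces the ITT result, and the re-applied lower limit in steps 5 and 6 is an added illustration.

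A reader might also infer that removal raises the rate by construction. That too is more than can be shown. The direction depends on the success rate and on centre sizes, and with no cap per site an unusually good large centre can reverse it. At 92% with uneven centres, removal moved a trial from pass to fail somewhat more often than from fail to pass (3.1% against 1.4% of triggered trials with sizes from 35 down to 5), though on few trials.

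A third reply is that the test level, the criterion for a responsible centre and extra sensitivity analyses belong in the SAP, and that centre models are already planned (9.3, 9.8.3). This is fair as to the missing detail, which is not counted here. It does not answer the two rules that section 9.3 does state: acceptability tied to non-rejection, and removal of centres selected on outcome. More detail in the SAP would leave both in place.

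**Conclusion.** The point holds in a limited form. Non-rejection of a test with about 15% power against one centre at 80%, and 37-38% against one at 70%, is weak grounds for calling the result acceptable. Removing centres chosen on their outcomes is biased towards a higher rate when success is near target, by about 2 to 3 points, with the exceptions shown above.

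The primary verdict is not at risk as the protocol is written. With identical centres at a true 85%, a reduced set that contradicts a failed verdict would arise in about 1-1.5% of all trials. That figure does not cover centres that truly differ. All simulated figures rest on the assumed 0.05 level, the centre layouts and the removal rule. This is a cheap improvement to how the centre effect is reported.

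**What to change.** In section 9.3, carried through to the SAP:

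1. State that the primary verdict uses all ITT patients from all centres, whatever the homogeneity test shows.
2. Delete the sentence that makes acceptability depend on non-rejection. The test can stay as a descriptive result.
3. Replace test-then-remove with a leave-one-centre-out table: for every centre in turn, the success rate and exact 95% confidence interval without it, always shown. Keep the planned centre model beside it.

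This meets the section's aim of seeing whether any one centre drives the result, without selecting on outcome. The cost is a few sentences and about eight re-runs of one estimate, with no change to sample size, data collection or the primary analysis.
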